5.13 Heart Rate Percentile

The heart rate percentile category will be derived based on the National Health Statistical Reports on resting pulse rate reference data for children, adolescents, and adults: United States, 1999-2008 (Ostchega et al. 2011). See Appendix 8 for details in deriving blood pressure percentile category adjusting for age and gender.

5.14 ECG Normal Ranges

The ECG normal ranges are provided in BMS UX023-CL301 CAMI 7 12-Lead ECG analysis plan (Version 1.0, 15APR2016). See [Appendix 9](#) for details in the normal ranges by age group and gender.

5.15 Adverse Events to Monitor

The definition for each type of adverse events to monitor is as the following:

- Injection Site Reaction is defined by preferred terms under the Medical Dictionary for Regulatory Activities (MedDRA) high-level term (HLT) “Injection site reaction”
- Hypersensitivity AE: Defined using relevant PTs in the narrow SMQs for “Hypersensitivity”.
- Hyperphosphataemia AE: Defined by using PTs: “Hyperphosphataemia”, “Blood phosphorus increased”, “Blood phosphorus abnormal”.
- Ectopic calcification related AE: There is no available SMQ. Ectopic calcification related AE is defined using a MedDRA search of ‘calcification’.
- Restless leg syndrome AE: Defined by PTs “Restless legs syndrome”, “Restlessness”, “Akathisia”, “Sensory disturbance”, “Psychomotor hyperactivity”, “Limb discomfort”, “Neuromuscular pain”, “Formication”.

See [Appendix 10](#) for the search criteria.

5.16 Dose-limiting Toxicity (DLT)

A DLT is defined as the occurrence of any of the following:

- Unexpected SAEs occurring during treatment considered to be either definitely, probably, or possibly related to the investigational product
- A confirmed serum phosphorus level of ≥ 6.5 mg/dL (defined as hyperphosphatemia) at any time after dosing

If a subject experiences a DLT, the planned dosing for that subject will be evaluated by the Investigator and Medical Monitor. The outcome of this investigation will determine the subjects’ continuation or withdrawal from the study.

If a subject continues to experience increases in serum phosphorus above the ULN (however do not meet the criteria for a DLT) despite dose reduction measures, the planned dosing for that subject will be evaluated by the Investigator and Medical Monitor. The outcome of this investigation will determine the subjects’ continuation or withdrawal from the study.

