- Chemistry, hematology, and urinalysis, including additional KRN23/XLH biochemical parameters of interest (serum 25(OH)D; lipase; amylase; creatinine; serum calcium and iPTH, and urinary calcium and creatinine)
- Anti-KRN23 antibody testing and dose-limiting toxicities
- Concomitant medications
- ECG

Exploratory Assessments:

- Health-related quality of life: Change from baseline in the SF-10 for Children Health Survey (SF-10; for subjects ≥ 5 years of age at the Screening Visit) at Weeks 24, 40, and 64
- Dental evaluation to assess the number of dental events such as dental caries, tooth extraction, root canal, dental abscesses, and gingivitis
- Pre- and post-prandial serum phosphorus and calcium concentrations at a single visit

Long-term Assessments in Treatment Extension Period:

- At Weeks 88, 112, and 140, efficacy, safety, pharmacokinetic, and exploratory assessments will be conducted as noted in the Schedule of Events.

Data Monitoring Committee

An independent DMC that includes members with expertise in metabolic bone disease, cardiology, and nephrology, and the conduct of clinical trials in children will act in an advisory capacity to monitor subject safety on a routine basis throughout the trial. The DMC will meet at least twice a year during the active-controlled period. The roles and responsibilities of the DMC will be defined in the DMC Charter.

STATISTICAL METHODS:

A full description of the statistical evaluations will be provided in the Statistical Analysis Plan.

Sample Size:

This Phase 3 study is powered to test the effect of KRN23 on improvement of rickets using RGI-C global score at Week 40 against the active control group based on the assumption of a mean RGI-C global score of 1.80 in the KRN23 group, 1.40 in the active control group, and a common standard deviation of 0.50. Given these assumption, a total sample size of 60 (30 per group) will provide approximately 80% power to detect such a difference in the mean RGI-C global score at Week 40 between treatment groups using a 2-sample t-test with a 2-sided alpha level of 0.05. A 10% drop-out rate is incorporated in the sample size calculation.

Efficacy Analysis:

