7.5.3 Safety Measurements

General assessments include Tanner staging for breast and testicular development, *PHEX* mutation analysis, medical history, and demographics. Safety will be evaluated by the incidence, frequency, and severity of adverse events (AEs) and serious adverse events

(SAEs), including clinically significant changes from baseline to scheduled time points in vital signs, weight, interval history and physical examination, eGFR, clinical laboratory evaluations (including additional KRN23/XLH biochemical parameters of interest), and concomitant medications. Ectopic mineralization safety assessments include renal ultrasound, echocardiogram (ECHO) and ECG, serum calcium and iPTH, and urinary calcium and creatinine. The development of anti-KRN23 antibodies and dose limiting toxicities (DLTs) will also be assessed. Refer to the Study Reference Manual for additional details on safety assessments.

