7.6.5 Safety Analyses

Full Analysis Set will be used for the safety analysis. Subjects will be analyzed based on the actual treatment received. Safety variables including AEs, SAEs, safety laboratory assessments, vital signs, renal ultrasound, ECG, ECHO, and anti-KRN23 antibody will be summarized descriptively by treatment group.

All AEs will be coded using the Medical Dictionary for Regulatory Activities (MedDRA). The incidence and frequency of AEs will be summarized by System Organ Class, Preferred Term, relationship to study drug, and severity. All reported AEs with onset during the treatment (ie, treatment-emergent AEs) will be included in the analysis. For each AE, the percentage of subjects who experienced at least 1 occurrence of the given event will be summarized by treatment group. Special attention will be given to those subjects who died, discontinued treatment due to an AE, or experienced a SAE.

Clinical laboratory data will be summarized by the type of laboratory test. Reference ranges and markedly abnormal results (specified in the SAP) will be used in the summary of laboratory data. The frequency and percentage of subjects who experience abnormal clinical laboratory results (ie, outside of reference ranges) and/or clinically significant abnormalities (as determined by the Investigator) will be presented for each clinical laboratory measurement. The SAP will provide additional details on the planned safety analyses.

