4.3 Safety Endpoints

Safety endpoints will be summarized at Baseline and at each observed time that they are collected. The following endpoints will be examined:

- Frequency (and %), and severity of adverse events (AEs) and serious adverse events (SAEs)
- Prior and concomitant medications
- Change from baseline to post-baseline visits in vital signs and weight
- Physical examinations
- Change from baseline to post-baseline visits in eGFR (calculated using the Bedside Schwartz equation)
- Shift from baseline to post-baseline visits in renal ultrasound in nephrocalcinosis score
- Change from baseline to post-baseline visits in Echocardiogram (ECHO)
- Change from baseline to post-baseline visits in chemistry, hematology, and urinalysis, including additional KRN23/XLH biochemical parameters of interest (serum 25(OH)D; lipase; amylase; creatinine; serum calcium and iPTH, and urinary calcium and creatinine)
- Shift from baseline to post-baseline visits in presence of anti-KRN23 antibody
- Change from baseline to post-baseline visits in Electrocardiogram (ECG)

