8.8.2 Clinical Laboratory Parameters

Descriptive statistics for clinical laboratory values and changes from the baseline values at each assessment time point will be presented by treatment group for laboratory parameters listed in [Appendix 2](#). Shift table for iPTH at each scheduled visit will be provided to assess to the normality over time. Listings for all clinical laboratory parameters and all abnormal laboratory parameters will be provided for each subject.

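### SAP 8.8.2 does not carry out the by-arm out-of-range laboratory counts in protocol 7.6.5, and no SAP table counts children with confirmed phosphorus of 6.5 mg/dL or more

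*SAP*

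**What the plan says.** On laboratory safety data, protocol 7.6.5 makes two commitments. "The frequency and percentage of subjects who experience abnormal clinical laboratory results (ie, outside of reference ranges") are to be shown for each test, together with abnormalities the investigator judges clinically significant. It adds: "Reference ranges and markedly abnormal results (specified in the SAP) will be used in the summary of laboratory data".

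SAP 8.8.2 plans descriptive statistics of values and changes by arm, a shift table for intact PTH only, and listings: "Listings for all clinical laboratory parameters and all abnormal laboratory parameters will be provided for each subject".

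The protocol treats dose-limiting toxicity as a safety assessment in the Synopsis ("Anti-KRN23 antibody testing and dose-limiting toxicities") and again in 7.5.3: "The development of anti-KRN23 antibodies and dose limiting toxicities (DLTs) will also be assessed". SAP 5.16 defines it by two limbs: unexpected, drug-related serious events, and "A confirmed serum phosphorus level of ≥ 6.5 mg/dL (defined as hyperphosphatemia) at any time after dosing". The SAP 4.3 endpoint list includes the antibody item ("Shift from baseline to post-baseline visits in presence of anti-KRN23 antibody") but has no entry for dose-limiting toxicity. Nor does the list of safety variables in SAP 8.8.

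SAP 5.15 monitors hyperphosphataemia as an adverse event: "Hyperphosphataemia AE: Defined by using PTs". SAP 8.8.1 tabulates the incidence of these events by arm.

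**The concern.** KRN23 works by raising serum phosphorus. The nonclinical summary in protocol 5.2.2 links soft-tissue and kidney mineralization to phosphate that stays too high, and protocol 7.4.1 withholds dosing once a child exceeds the upper limit of normal for age. The safety objective is a comparison with active control. How many children overshoot in each arm is therefore a basic safety result, and the SAP plans no table that gives it from laboratory values.

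What remains is a count of reported events. Under protocol 7.5.3.13 a laboratory change becomes an adverse event only if the investigator judges that it should, and investigators in this open-label trial know the treatment. The tables for calcification events, renal ultrasound and echocardiography cover a possible later consequence, not the phosphorus excursion itself.

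**Working it through.** The plan states no figure here to reproduce. The check compares text, with two short counts.

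**Step 1: commitment against delivery.** Phosphorus is among the tests covered by the 7.6.5 commitment (protocol Table 7.5.3.8.1; SAP Appendix 2). SAP 8.8.2 contains no number and percent out of range. Partial cover exists for intact PTH (shift table) and for phosphorus and TmP/GFR (in-range proportions, SAP 8.5.4.7), so the counts are missing for most tests, not literally all. No markedly abnormal laboratory limits appear: Appendix 2 lists analytes only, and the only significance limits in the SAP are the ECG limits in Appendix 9.

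**Step 2: can any planned output give the number of children with high phosphorus?**

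| SAP output | What it gives | Why it is not the count |
|---|---|---|
| 8.8.2 and 8.5.4.7 statistics by arm and visit | Quartiles and maximum | Shows whether any used value was high, not how many children. Under 7.2.3 a scheduled value displaces an unscheduled one at the same visit, so repeats can drop out |
| 8.5.4.7 proportion within 3.2 to 6.1 mg/dL, by visit | Number in range | The remainder mixes low with high values; values above 6.1 but below 6.5 are not dose-limiting |
| 8.8.1 hyperphosphataemia events | Children with a reported term | Depends on the investigator's decision to report |
| 8.8.1 serious and related events | Largely covers the serious-event limb | Does not cover the laboratory limb |
| Listings | Every value | No count by arm and no rule for what counts as confirmed |

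As an example of the second row, take 30 children with 20 in range. Ten low and none high gives 20/30 = 66.7%; eight low and two high gives the same 66.7%. The maximum would separate those two cases, but would not separate one high child from three.

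**Step 3: the event term list.** SAP 5.15 names three preferred terms: hyperphosphataemia, blood phosphorus increased and blood phosphorus abnormal. Appendix 10 names only the first two.

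**Step 4: sampling by arm.** From protocol Tables 2.1 and 2.2, scheduled post-baseline phosphorus draws on KRN23 are at Weeks 1, 2, 4, 8, 12, 16, 24, 32, 33, 40, 52 and 64, which is 12. Footnote 4 gives control visits at Weeks 1, 4, 8, 16, 24, 32, 40, 52 and 64, which is 9. The difference is 12 − 9 = 3 (Weeks 2, 12 and 33). To Week 40 it is 10 against 7. Protocol 7.4.1 adds unscheduled draws on KRN23 for dose management. This matters only for the design of the table proposed below.

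**Step 5: likely scale.** Protocol 5.2.3 reports no child above normal in the Phase 2 interim analysis of the first 36. Taking 36 as the denominator, the exact 95% upper limit is 1 − 0.025^(1/36) = 9.7%, and 9.7% of 30 is 2.9. Zero to about three children on KRN23 is therefore compatible with that experience, although Phase 2 had an older age range and two dosing intervals. Zero of 30 in this trial would have an upper limit of 1 − 0.025^(1/30) = 11.6%. The documents give no comparable figure for the control arm.

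**The case against.** The strongest reply is that the protocol already plans the counts. Section 7.6.5 includes phosphorus among the tests, and 7.6.3 says the SAP expands the protocol analyses and that departures will be noted in the study report. SAP silence does not cancel a protocol commitment. This stands: a reader might infer that out-of-range counts are planned nowhere, and the documents do not support that. The SAP was also written to the original protocol of 04APR2016, whereas the protocol at hand is Amendment 1. The supplied summary of changes records no change to the laboratory paragraph, so this is only a caveat.

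Second, dose-limiting toxicity works mainly as a rule for managing individual children. It goes to the investigator and medical monitor, and the data monitoring committee sees aggregate safety data. The serious-event limb is largely covered by the serious and related event table, so it would be too strong to say that dose-limiting toxicities go uncounted altogether. The gap is the laboratory limb.

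Third, nothing is lost. Listings and safety shift tables keep all values, and in about 60 children a count could be made at reporting. That is correct, but the count would then be made with the data in view and with no rule for confirmation or unequal sampling.

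Two further inferences are tempting. One is that the extra KRN23 draws already bias the plan against KRN23. No current table counts children by any high value, so there is nothing yet to bias; the size in a future table would depend on per-draw risk and within-child correlation, which the documents do not give. The other is that open-label reporting hides KRN23 excursions. The documents show that reporting is discretionary, not in which direction it would err.

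**Conclusion.** The point holds as a minor gap in safety reporting. SAP 8.8.2 does not carry out the by-arm out-of-range counts in protocol 7.6.5, and no SAP table counts children meeting the phosphorus criterion in 5.16. The SAP's only by-arm count of high phosphorus rests on investigator-reported terms under two conflicting lists.

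The expected numbers are small, perhaps zero to three children per 30 on KRN23 if Phase 2 is a guide. Even a zero is worth stating with its interval. Efficacy results are unaffected, and the conclusion rests on comparing the two documents, not on any assumed rate.

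**What to change.** 1. Add to SAP 8.8.2 one table by arm, to Week 40 and to Week 64, from central-laboratory values, with number and percent of children who have:
   - any post-baseline phosphorus above the age-specific upper limit used for dose withholding in protocol 7.4.1;
   - any value of 6.5 mg/dL or more;
   - a value of 6.5 mg/dL or more confirmed by a repeat sample.

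   State the confirmation rule, and do not let it require the value to persist after a dose has been withheld. Any value above the upper limit triggers withholding, so a persistence rule would tend to undercount on KRN23. One option is a repeat taken before the first withheld dose was due.

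   Show the table for all values including unscheduled ones, and again for the nine visits both arms share.

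2. Carry the number and percent below and above the reference range into 8.8.2 for the other Appendix 2 tests. Either set the markedly abnormal limits that the protocol leaves to the SAP or state that none will be used.

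3. Use the three-term hyperphosphataemia list in both 5.15 and Appendix 10.

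The cost is one or two extra tables, with no new visits or samples. The phosphorus table needs a footnote saying that fasting samples may miss peaks after oral phosphate in the control arm.

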5.17 Duration of Conventional therapy before Baseline

The conventional therapy that subjects received before baseline will be identified by reviewing prior medication data.

The definition for duration of conventional therapy a subject received before baseline is as follows:

Duration of conventional therapy = End date of the latest conventional therapy taken - start date of earliest conventional therapy taken prior to randomization

If the date is partially or completely missing, apply the following imputation rule:

Start Dates

- If the FIRST start date of conventional therapy is completely missing, then use the next earliest non-missing date.
- If the year is known and month is missing, then assign 'January 1st';
- If the year and month are both known and day is missing, then assign the first day of the month.

Stop Dates

- If LAST stop date is completely missing, then impute 'one day' prior to the randomization date
- If year is known the month is missing, then assign "December 31th". If this imputed date is after randomization date, use one day prior to randomization date instead.

If year and month are both known and the day is missing, then assign the last day of the month. If this imputed date is after randomization date, use one day prior to randomization date instead.

6 ANALYSIS POPULATIONS

6.1 Screened Population

The Screened Population will consist of all unique subjects who underwent a Screening Visit and received a subject identification number.

6.2 Full Analysis Set (FAS)

The Full Analysis Set will consist of all randomized subjects who received at least one dose of assigned medication and had at least one post-baseline assessment. Subjects will be analyzed according to the assigned treatment at randomization.

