The Full Analysis Set will include all randomized subjects who received at least 1 dose of assigned medication, and the Full Analysis Set will be used for both efficacy and safety analyses. For efficacy analyses, subjects will be analyzed by the randomized treatment group. The primary efficacy endpoint will be tested to compare the mean RGI-C global score between the KRN23 and active control groups.

At the Week 40 Analysis (the primary efficacy analysis time point), the primary hypothesis of the primary endpoint is to test whether there is a difference between the KRN23 and active control groups in the mean RGI-C global scores at Week 40. An Analysis of Covariance (ANCOVA) model with treatment group adjusting for baseline rickets severity and age will be used to test this hypothesis at a 2-sided alpha level of 0.05. The proportion of RGI-C responders will be summarized for each treatment group.

At the Week 64 Analysis (secondary analysis), RGI-C global score over time will be analyzed using the repeat measurement model that includes treatment group, visit, treatment group by visit interaction, and adjusted for baseline rickets severity and age.

The change from baseline in RSS total score over time will be analyzed using the same method as that of the RGI-C global score.

Analyses of other efficacy and PD measures will be performed at Week 40, Week 64, and Week 140. Endpoints will be summarized descriptively by each treatment group. Treatment comparison will be performed using the repeat measurement model including treatment group, visit, treatment group by visit interaction, adjusting for baseline age, rickets severity. Other baseline covariates may be considered for adjustment.

Safety Analysis:

Full Analysis Set will be used for the safety analysis. Subjects will be analyzed based on the actual treatment received. Safety variables including AEs, SAEs safety laboratory assessments, vital signs, renal ultrasound, ECG, ECHO, and anti-KRN23 antibody will be summarized descriptively by treatment group.

Table 2.1: Schedule of Events – Treatment Period Weeks 1-30

VISIT ID	Screening/ Baseline ¹		Treatment Period															
	SV	BL V1	V2	H H V3	V4	HH V5	V6	HH V7	HH V8	HH V9	V10	HH V11	HH V12	HH V13	V14	HH V15	HH V16	HH V17
TIME (WEEK/DAY)	W-8 to BL	W0	W1	W2	W4	W6	W8	W1 0	W12	W14	W16	W18	W20	W22	W24	W26	W28	W30
Informed Consent	X																	
Inclusion/Exclusion	X	X																
Medical History, Demographics	X																	

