7.6.3 General Principles

A general description of the statistical methods to be used to analyze the efficacy and safety of KRN23 is outlined below. The analyses planned in this protocol will be expanded in the SAP to include detailed description of the analyses. The SAP will be finalized and approved prior to the database lock. Any deviations from the analyses described in the protocol and SAP will be noted in the final clinical study report.

The completeness of the data affects the integrity and accuracy of the final study analysis. Therefore, every effort will be made to ensure complete, accurate and timely data collection, and to avoid missing data. The procedures for handling missing, unused, or spurious data, along with the detailed method for analyses will be presented in the SAP.

The statistical analyses will be reported using summary tables, figures, and data listings. Descriptive statistics will be used to summarize the data. For continuous variables, the mean, standard deviation, median, quartile, minimum, and maximum will be provided. For discrete data, the frequency and percent distributions will be provided.

Full analysis set will include all randomized subjects who received at least 1 dose of assigned medication, and full analysis set will be used for both efficacy and safety analyses.

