7.6.3.1 Subject Accountability

The number of subjects randomized, who complete the study, and discontinue the study will be summarized. The reason for study treatment discontinuation and study discontinuation will also be summarized.

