8.2 Subject Accountability

The number and percentage of subjects in each of the analysis populations (Screened, Full, PK and PD) will be summarized by treatment group. Subjects and their data excluded from any analysis set will be listed.

Screen-failure subjects (ie, subjects screened but not randomized) and the associated reasons for failure to randomize will be tabulated overall for the Screened Population. The number and percentage of subjects who complete the treatment period and of subjects who prematurely discontinue will be presented for each treatment group and pooled across treatment groups for the Full Analysis set. The reasons for premature discontinuation from treatment period as recorded on eCRFs will be summarized.

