8.5 Efficacy Analysis

The efficacy analyses will be based on the Full Analysis Set.

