8.5.2 Sensitivity Analysis for Missing Data

Sensitivity analyses to assess the robustness of the primary analysis result to missing data will be conducted on RSS and RGI-C endpoints. Theses may include, but are not limited to:

- Last Observation Carried Forward (LOCF): the last non-missing post-baseline observation will be carried forward to the corresponding endpoint for evaluation. If no post-baseline observation is available, the baseline observation will be used for evaluation; if no baseline is available, the LOCF approach will not be performed.
- Multiple imputation (MI): the PROC MI procedure in SAS will be utilized to impute missing values using a Markov Chain Monte Carlo (MCMC) approach by 100 times. The imputed dataset will be analyzed by the ANCOVA model at Week 40 analysis or GEE model at Week 64 analysis, the results will be combined using the PROC MIANALYZE procedure in SAS. Baseline RSS total score, treatment group and baseline age stratification factor will be used as predictor variables in the imputation. Other variables such as change from baseline in ALP may also be considered as a predictor variable.

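### The SAP's Full Analysis Set is narrower than the protocol's and carries the discontinuation table, so the earliest losses can be missing from the by-arm rates

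*SAP*

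**What the plan says.** The protocol defines the set twice in the same way. The synopsis states: "The Full Analysis Set will include all randomized subjects who received at least 1 dose of assigned medication". Section 7.6.3 repeats it: "Full analysis set will include all randomized subjects who received at least 1 dose of assigned medication".

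SAP 6.2 adds a second condition. Its set is the randomized subjects who "received at least one dose of assigned medication and had at least one post-baseline assessment". It gives no reason and does not say what kind of assessment counts. SAP 6.3 defines the Safety Analysis Set by randomization and one dose alone, so the extra condition applies to the efficacy set only.

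On disposition, protocol 7.6.3.1 says: "The number of subjects randomized, who complete the study, and discontinue the study will be summarized". SAP 8.2 says that "subjects who prematurely discontinue will be presented for each treatment group and pooled across treatment groups for the Full Analysis set". SAP 8.3 (deviations), 8.4.1 (exposure), 8.4.2 (compliance) and 8.4.3 (demographics and baseline) use the same set.

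On efficacy, SAP 8.5 says: "The efficacy analyses will be based on the Full Analysis Set". This covers the missing-data sensitivity analyses in 8.5.2, where "the PROC MI procedure in SAS will be utilized to impute missing values".

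**The concern.** Under SAP 6.2, membership of the analysis set depends on something that happens after randomization. Allocation is open, and inclusion criterion 6 requires every child to have been on oral phosphate and active vitamin D already, so a control family returns to a treatment it knows. Very early withdrawal could therefore differ between arms. If it did, the discontinuation table is where a reader would look first.

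As written, that table cannot show a dosed child who left before any post-baseline assessment. It also cannot show a child who was randomized and never dosed. The screen-failure table does not pick up either child, because it covers only subjects who were screened and not randomized. What is at stake is the accuracy of the reported by-arm discontinuation rate, together with a mismatch between SAP and protocol on who is in the main analysis set.

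**Working it through.** **1. The plan's own figures.** Protocol 7.6.1 and SAP 3.5 give means of 1.80 and 1.40, SD 0.50, two-sided alpha 0.05, about 80% power, 30 per arm and 10% dropout.

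- Standardized difference: (1.80 − 1.40)/0.50 = 0.8.
- Two-sample t-test, 80% power: 25.5, so 26 per arm.
- With 10% dropout: 26/0.90 = 28.9, so 29 per arm and 58 in total, against the stated 60.
- With 30 per arm less 10%, 27 are evaluable and power is 82.2%.

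The sample size reproduces to within two subjects. This point does not dispute it; 30 per arm and 10% dropout (3 per arm) are used below.

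**2. Who is in which set, reading SAP 6.2 literally.**

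| Child | Protocol FAS | SAP FAS | SAP Safety Set | All randomized |
|---|---|---|---|---|
| Randomized, never dosed | no | no | no | yes |
| Dosed, no post-baseline assessment | yes | no | yes | yes |
| Dosed, lost after a first post-baseline assessment | yes | yes | yes | yes |

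The SAP and protocol definitions differ only in the second row. The first row is missing under both definitions.

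**3. How early the loss must be.** Protocol Table 2.1 schedules serum phosphorus, 1,25(OH)₂D, weight, adverse events and concomitant medication at Week 1. Footnote 4 has control subjects in clinic at Week 1 as well. Any one of these measurements would satisfy the literal wording, so the second row is limited to children lost before about Week 1.

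**4. Effect on the discontinuation table (illustration).** The documents give no number of such children. Assume 30 in an arm and 3 dropouts, of whom k had no post-baseline assessment. The rate shown on the SAP's set is (3 − k)/(30 − k).

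| k | Shown under SAP 8.2 | All randomized |
|---|---|---|
| 0 | 3/30 = 10.0% | 3/30 = 10.0% |
| 1 | 2/29 = 6.9% | 3/30 = 10.0% |
| 2 | 1/28 = 3.6% | 3/30 = 10.0% |
| 3 | 0/27 = 0% | 3/30 = 10.0% |

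With k = 1 in one arm and k = 0 in the other, two arms that each lost 3/30 would appear to differ by 10.0 − 6.9 = 3.1 percentage points. The k = 3 row marks the end of the range and is not an expectation: it needs every dropout in the arm to occur before about Week 1.

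The same arithmetic holds for a randomized child who was never dosed, but the protocol's FAS would then also give 2/29. Only an all-randomized denominator gives 3/30.

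**5. Effect on the efficacy analyses.**

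- *Week 40 ANCOVA (SAP 8.5.3).* No imputation is stated. A child without a Week 40 RGI-C score contributes nothing under either definition, so the change is nil.
- *Multiple imputation (SAP 8.5.2).* The named predictors are baseline RSS total score, treatment group and age stratum, with change in ALP as an option. A child with no post-baseline data has no ALP change, so the imputed score comes from the model fitted to observed children with the same arm and baseline values. The expected treatment difference is essentially unchanged.
- *LOCF (SAP 8.5.2).* The fallback reads: "If no post-baseline observation is available, the baseline observation will be used for evaluation". RGI-C is itself a change score, so there is no baseline value to carry forward. For RSS, a restored child would enter with zero change. The plan states no assumed RSS change, so this cannot be sized, but it affects only a sensitivity analysis and the same few children.

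**The case against.** The strongest reply is that the excluded group is nearly empty and that the SAP discloses it. The condition is not tied to a radiograph, and both arms have a Week 1 visit. The LOCF fallback itself anticipates subjects with no post-baseline observation on the endpoint, which fits a set that admits children on the strength of other assessments. SAP 8.2 counts the Full set by treatment group and lists subjects excluded from any analysis set. SAP 6.3 keeps every dosed child for safety, and 8.8.1 tabulates adverse events leading to discontinuation of study and of treatment on that set. Differential withdrawal in the first days is a conjecture, and a family unhappy with its allocation might equally leave before the first dose, which the protocol's own FAS would not capture either.

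Most of this stands, and it sets the size of the point. Three things remain. The two documents define the same set differently, with no reason given. A listing does not replace a by-arm discontinuation rate, and the population count in SAP 8.2 names the Screened, Full, PK and PD sets but no randomized set. And the case of the undosed child argues for an all-randomized disposition table, not for leaving SAP 8.2 as it is.

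The SAP cites the original protocol of 04APR2016, and the protocol in hand is Amendment 1. The amendment's summary of changes, as supplied, lists no change to the Full Analysis Set, so version drift does not evidently explain the difference.

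**Conclusion.** The inconsistency is real and its consequence is small. The SAP's Full Analysis Set is narrower than the protocol's, and SAP 8.2 builds the discontinuation table on it although protocol 7.6.3.1 starts from subjects randomized. The by-arm discontinuation rate, and the deviation, exposure, compliance and demographic tables, can therefore omit a dosed child lost before about Week 1 and any randomized child never dosed. One such child among three dropouts moves the shown rate from 10.0% to 6.9%. That rests on an assumed 30 per arm, 3 dropouts and k = 1, and on the literal reading of an assessment.

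A reader might infer three stronger things that the documents do not support.

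- *That early dropout is concealed.* Exclusions are listed, the Full set is counted by arm, and dosed children stay in the safety tables.
- *That the missing-data analyses are undermined.* Multiple imputation from arm and baseline values would give nearly the same estimate with these children included. It would not detect informative early withdrawal in either case. Scoring three lost children as no change would move the planned 0.40 difference to 1.80 × 27/30 − 1.40 = 0.22 (all in the KRN23 arm) or 1.80 − 1.40 × 27/30 = 0.54 (all in control), but no planned RGI-C analysis scores them that way.
- *That the condition removes everyone without a post-baseline X-ray.* SAP 6.2 does not say so, and the LOCF fallback suggests otherwise.

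**What to change.** 1. In SAP 6.2, delete the post-baseline-assessment condition, so that the Full Analysis Set is all randomized subjects with at least one dose, as in the protocol.
2. In SAP 8.2, base the completion and discontinuation table on all randomized subjects by arm, with a line for those randomized and not dosed. The first change does not bring those children back.

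The multiple imputation, the LOCF analysis and the other tables on the Full Analysis Set then follow the restored definition with no further edit. The cost is one sentence in 6.2, one in 8.2, and the table denominators. No new data are needed, and the primary result does not change.
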